To estimate the budget impact of CT/NG testing among asymptomatic pregnant women, we will combine the total recurrent costs with capital, training, and start-up costs. Next, we will build a decision analytic model to estimate the cost per pregnant woman tested, tested positive, treated, and cured by time of delivery. If the intervention is effective, we will calculate the incremental costs per adverse neonatal outcome averted (e.g. neonatal CT/NG infections, preterm birth, and low birth weight) comparing the testing intervention with syndromic management. We will also estimate a cost-effectiveness ratio (ICER, difference in costs divided by difference in health outcomes), representing the change in costs per averted DALYs associated with preterm birth/low birth weight infants.

We will also perform a probabilistic uncertainty analysis where parameters are randomly sampled from probabilistic distributions to generate 10,000 parameter sets. For each parameter set, the model will run and produce a distribution of outcomes. We will provide the means and 95% confidence intervals for all cost and health outcomes. If the intervention is effective, we will also calculate mean incremental cost-effectiveness ratios (ICER; \$/ DALY averted) compared to syndromic management, assessing cost-effectiveness under a willingness-to-pay threshold informed by the WHO's Gross Domestic Product / capita threshold, which was US\$7,961 in Botswana 2019. We will also calculate the probability that the scenarios are cost-effective by assessing the proportion of ICERs that fall below the willingness to pay threshold.(3)

Sensitivity analyses will be conducted through one-way and multi-way methods to identify key cost drivers and assess how changing parameters impacts the overall costs and per patient cost of each strategy.(4)

Sample size

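### Counting ICERs below the threshold misclassifies every simulation draw with negative DALYs averted, so the planned probability of cost-effectiveness can be wrong

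*SAP*

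**What the plan says.** The relevant text is in the economic paragraphs of the SAP's Statistical analysis section.

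- The ratio is defined as "ICER, difference in costs divided by difference in health outcomes", with the health outcome expressed per DALY averted: "representing the change in costs per averted DALYs associated with preterm birth/low birth weight infants".
- In the uncertainty analysis, "parameters are randomly sampled from probabilistic distributions to generate 10,000 parameter sets", the model is run on each set, and "We will provide the means and 95% confidence intervals for all cost and health outcomes".
- On condition that the intervention is effective, "we will also calculate mean incremental cost-effectiveness ratios" against syndromic management, "assessing cost-effectiveness under a willingness-to-pay threshold informed by the" WHO GDP-per-capita figure, "which was US\$7,961 in Botswana 2019".
- The next sentence gives the decision rule: the analysts will calculate "the probability that the scenarios are cost-effective by assessing the proportion of ICERs that fall below the willingness to pay threshold".

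The section has no net-benefit calculation, no dominance rule and no handling of draws in which DALYs averted are negative or near zero. It does not say by what criterion the intervention would be judged effective. It also does not say whether the mean ICER is an average of per-draw ratios or a ratio of two averages.

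**The concern.** An ICER of −5,000 can come from a draw in which testing saves money and improves health, or from one in which it costs more and worsens health. Both fall below a positive threshold, so the stated rule counts both as cost-effective. Likewise, a positive ICER can mean paying for health gain or saving money at the expense of health, and for these two cases the threshold should be applied in opposite directions.

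The rule therefore works only where every draw shows health gain, and the SAP does not ensure that. If testing costs more in every draw, the reported probability is too high by the share of harmful draws. If testing saves money, it can be too low. The error comes from the rule, so more draws will not reduce it.

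The primary outcome is not affected. The probability of cost-effectiveness is nevertheless one of the figures a ministry would look at, and Protocol section 11(d) names antenatal care policies, guidelines and funding levels among the things the study should inform.

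A related but lesser matter is the mean ICER. Read as the average of per-draw ratios, it is unstable whenever DALYs averted can fall near zero.

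**Working it through.** **Inputs from the SAP.** Threshold L = US$7,961 per DALY averted (the only figure given); 10,000 parameter sets; the ICER definition and decision rule quoted above. The SAP states no probability of cost-effectiveness that could be reproduced.

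**Inputs not in the documents.** Incremental cost per woman, DALYs averted per woman and their distributions. All values used for these below are assumptions.

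**Step 1: algebra, which needs no assumed input.** Let c be incremental cost and d be DALYs averted. A draw is cost-effective when net benefit L × d − c > 0.

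- If d > 0, then c/d < L is equivalent to L × d − c > 0. The rule is right.
- If d < 0, multiplying through by d reverses the inequality, so c/d < L is equivalent to L × d − c < 0. The rule is wrong.

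Hence the misclassified share is P(d < 0), and

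net error = P(d < 0 and net benefit < 0) − P(d < 0 and net benefit > 0),

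which lies between −P(d < 0) and +P(d < 0). If c > 0 in every draw, no harmful draw has positive net benefit and the error is exactly +P(d < 0). A check on 1,000,000 random pairs (c, d) at L = 7,961 gave 100% disagreement with net benefit when d < 0 and 0% when d > 0.

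**Step 2: single draws at L = 7,961.**

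| c (US$) | d (DALYs) | ICER | Net benefit | SAP rule | Correct? |
|---|---|---|---|---|---|
| +25 | +0.005 | 5,000 | 39.8 − 25 = +14.8 | accept | yes |
| +25 | −0.005 | −5,000 | −39.8 − 25 = −64.8 | accept | no |
| −25 | −0.005 | 5,000 | −39.8 + 25 = −14.8 | accept | no |
| −25 | −0.001 | 25,000 | −8.0 + 25 = +17.0 | reject | no |

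**Step 3: illustrative size.** Assume d is normal with mean 0.005 and SD 0.005/z, where z = 1.645, 1.96 or 2.5 gives 5%, 2.5% or 0.6% harmful draws. Cost is normal. Each cell shows the SAP rule, then net benefit (4 million draws).

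| Cost, mean (SD), US$ | 5% harmful | 2.5% harmful | 0.6% harmful |
|---|---|---|---|
| +25 (4) | 77.7% / 72.7% | 78.8% / 76.3% | 82.2% / 81.6% |
| 0 (10) | 96.3% / 93.6% | 97.2% / 96.1% | not run |
| −25 (4) | 95.4% / 99.6% | 97.6% / 99.9% | 99.4% / 100.0% |

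Reconciliation with step 1 at 5% harmful:

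- Cost-neutral case: 2.50% costlier-and-worse draws accepted, 1.36% cheaper-but-worse wrongly accepted and 1.13% wrongly rejected sum to 4.99%, against 5.00% with d < 0. The net error is 2.50 + 1.36 − 1.13 = +2.7 points.
- Saving case: 0.41% wrongly accepted and 4.57% wrongly rejected sum to 4.98%, against 4.98% with d < 0. The net error is 0.41 − 4.57 = −4.2 points.

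**Step 4: sensitivity to the threshold, 5% harmful.** At half, one and three times US$7,961 the error is +5.0 points each time when testing costs US$25 more, and −5.0, −4.2 and −0.3 points when it saves US$25.

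**Step 5: when the error vanishes or grows.** With lognormal d (mean 0.005, coefficient of variation 1/1.645, so never negative) and cost +25 (4), both rules give 70.8%. At the other end, suppose the effect on preterm birth/low birth weight is sampled with the uncertainty of 232 women per arm (SAP, Sample size), with assumed control risk 15% or 25% and relative risk 0.70 to 0.95. Harmful draws then make up 2.2% to 40.7%. In one such case (risk 15%, relative risk 0.85, 5 DALYs per case, US$60 per woman), 24.0% of draws are harmful and the rule gives 98.6% against 74.5%.

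**Step 6: mean ICER.** With cost +25 (4), 5% harmful draws and 10,000 draws per run, three sets of 1,000 seeds gave a negative average of per-draw ratios in about 12% to 14% of runs. It exceeded US$7,961 in about 28% to 31% of runs. The ratio of means stayed between roughly 4,900 and 5,100, against an assumed true value of 25/0.005 = 5,000.

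**The case against.** The algebra is hard to dispute, so the case on the other side is about consequence.

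- **No size can be derived.** The SAP gives no distributions. Its decision model runs from testing to treatment to cure and may never produce negative DALYs averted, in which case the error is nil. This stands: the flaw is certain in the rule but conditional in its effect.
- **The effectiveness condition may screen out harm.** The ICERs being counted may be those calculated only if the intervention is effective. If that meant demonstrated benefit, harmful draws would probably be few and the error small (2.5 points at 2.5% harmful, 0.6 at 0.6%, with US$25 extra cost). This stands in part, and it is why the 24.0% and 40.7% figures, which apply no such condition, show only an upper range. But the condition has no criterion and does not act draw by draw. An intervention that is effective on average can still give harmful draws. If effectiveness is judged on vertical transmission, that need not constrain the DALYs in the ICER, which are tied to preterm birth and low birth weight.
- **Cost savings are hypothetical.** The SAP describes adding recurrent, capital, training and start-up costs and mentions no offset in that calculation. If testing always costs more, the error is upward only. This is fair; the cost-neutral and saving rows show how the rule behaves and are not forecasts.
- **The mean ICER is an ambiguity.** The text does not commit to averaging ratios, and the promised means of costs and health outcomes would let a reader form the ratio of means. This stands. Those means would not, however, let a reader recover the correct probability.
- **The analyst would use net benefit anyway.** Perhaps, but the plan writes down a different rule, and a methods reference placed after it does not replace it.

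**Conclusion.** The concern holds. As written, the rule gives the wrong answer for every draw with negative DALYs averted and the right answer for every draw with positive DALYs averted, whatever the costs and for any positive threshold. That part rests on no assumption.

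The numerical effect cannot be fixed from the documents. It is zero if the sampled distributions exclude harm. Otherwise it is at most the share of harmful draws, and equals that share, upward, if testing costs more in every draw. The 77.7% against 72.7% comparison rests on an assumed mean of 0.005 DALYs averted, normal uncertainty, US$25 extra cost and 5% harmful draws.

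The result affected is supplementary. The plan should be corrected because the stated rule is wrong and the correction is nearly free. The undefined mean and the undefined effectiveness condition are missing detail rather than demonstrated errors, and can be settled in the same edit.

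**What to change.** In the economic paragraphs of the SAP's Statistical analysis section:

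1. Define the probability of cost-effectiveness as the share of all 10,000 parameter sets in which (threshold × DALYs averted) − incremental cost > 0, at whatever threshold the plan adopts. Do not drop draws with negative DALYs averted.
2. Define the reported ICER as mean incremental cost divided by mean DALYs averted over the same parameter sets.
3. State the criterion for regarding the intervention as effective, including the outcome on which it is judged.

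This takes two or three sentences and needs no new data and no further simulation. The reported probability may rise, fall or stay the same; if no draw has negative DALYs averted, it does not change.

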### 3. Study Design

**Specific Aim 1: To determine the burden of CT and NG infections and correlates of infection among asymptomatic pregnant women in Gaborone, Botswana.**

Title: The diagnosis and treatment of *Chlamydia trachomatis* and *Neisseria gonorrhoeae* in pregnant women to prevent adverse neonatal consequences."

**Methods and Procedures:** To accomplish Aim 1, we will conduct a cohort study among antenatal patients at collaborating Greater Gaborone District Health Management Team (DHMT) clinic sites (STI testing clinics). First, 1(a): Use diagnostic testing to estimate the prevalence of CT/NG infections at the 1st antenatal care visit, a 3rd trimester visit, and the 1st postnatal care visit; and estimate the incidence of infections between visits. 1(b): To assess the correlates of infection, including sociodemographic and behavioral factors (e.g. alcohol use), obstetric and medical information (e.g. HIV status), sex partner characteristics, and partner notification and treatment outcomes.

**Recruitment and Eligibility:** We will recruit 250 study participants from pregnant women presenting for antenatal care services at designated study 'testing' clinics in Gaborone. Eligibility/Inclusion criteria (also described in Section E) include: 1) Age  $\geq$  15 years, 2) Currently pregnant, 3) Attending first ANC visit, 4) 27 weeks of gestation or less, 5) Not currently experiencing CT/NG-related symptoms (determined by validated screening tool), 6) Not treated for CT/NG in the past 30 days 7) Willingness to provide self-collected specimens for CT/NG testing (at three time points), 8) Willingness to return for a test of cure (if test positive during antenatal care), 9) Will reside in Gaborone through the time of delivery and 1st postnatal visit, 10) Willingness to have neonates tested for CT/NG at their first postnatal visit, And 11) Mentally competent to understand the informed consent.

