**Data collection:** Participants will be asked to respond to a survey on socioeconomic characteristics, relationship status and sexual history (e.g. number of condomless sex acts), other risk behaviors (e.g. alcohol use), obstetric/medical history, and prior STI symptoms and treatment in the past year. A sub-set of participants will be asked additional questions on partner notification and treatment experiences postnatally. A data collection instrument will be used to abstract obstetric, and medical information from the patient-held and clinic records, including receipt of syphilis testing, results and titre, and treatment.

The sample of sex partners will participate in a brief semi-structured interview on partner notification and treatment experiences. The sample of stakeholders will participate in a brief semi-structured interview on antenatal diagnostic testing for chlamydia and gonorrhea, point-of-care syphilis testing, and STI expedited partner therapy.

Specific Aim 2: To compare longitudinal neonatal outcomes for pregnant women tested & treated for CT/NG infections with women who received standard antenatal care.

**Methods and Procedures:** Simultaneously with Aim 1, 250 antenatal patients at designated study 'standard of care' clinics will be enrolled as a comparison group receiving the standard care with additional partner services. At standard of care clinics, CT/NG testing will be offered to mothers and neonates at the 1st postnatal visit for all 500 participants to accomplish 2(a): To estimate the frequency of vertical transmission of CT/NG infections and adverse neonatal outcomes and association with maternal testing and treatment. And subaim 2(b): To assess independent factors associated with adverse neonatal outcomes and control for these factors in the analysis. Exposure measures will include maternal sociodemographic, behavioral, obstetric, and medical information, and partner treatment, and adverse perinatal outcomes (e.g. low birth weight).

Title: The diagnosis and treatment of *Chlamydia trachomatis* and *Neisseria gonorrhoeae* in pregnant women to prevent adverse neonatal consequences.”

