Prevalence of each STI will be measured as the proportion of individuals testing positive for a given STI divided by the number of individuals tested at each time point. Exact binomial 95% confidence intervals for prevalence will be estimated. Incident infections will be identified when a participant tests negative for an STI during her first ANC visit and positive for an STI during follow-up visits. Time at risk will be the length of time between the first test date and the positive test date. Correlates of CT/NG infections will be identified using both bivariate analyses and multivariate analyses.

Our primary outcome (mother-to-child transmission of CT and NG) and secondary outcomes (composite of preterm birth and/or low birth weight, and prevalence of maternal CT/NG infection at delivery) will be assessed using intention to treat analysis at the clinic level. We will conduct both unadjusted and adjusted analyses, including risk factors for maternal STI and neonatal infection that may be imbalanced between the testing and standard-of-care clinics. Effect measures will be estimated with 95% confidence intervals. All analyses will be carried out using the latest version of Stata statistical software (17.0 or higher; College Station, TX, USA).

To assess immune/inflammatory markers, multiple logistic regression models will be developed in an iterative process to identify individual cytokines and groups of cytokines associated with mother-to-child

transmission of CT/NG, preterm birth, and low birth weight. Additionally, we will identify plasma cytokine signatures that classify study participants with or without preterm birth/low birth weight infants.(1) We will define three equal frequency tertiles or “bins” (low, medium, and high), using all plasma samples. Next, we will use the VSURF R package, a random forest method to select the most predictive cytokines to differentiate samples from participants with and without preterm birth/low birth weight infants.(2) From these, we will build a decision tree to classify the samples. To better calibrate the accuracy of the decision tree, we will perform permutation testing.

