The sample size of 500 participants was determined to have sufficient power to detect a difference in rates of vertical transmission of CT and NG based on 1) the prevalence of CT and/or NG among pregnant women in Botswana (10%),(5) and 2) the risk for vertical transmission of CT/NG to newborn infants during parturition (50%).(49-52). Antenatal CT/NG testing and treatment is expected to reduce vertical transmission by over 85%, from 5% in the control to 0.7% in the intervention group.(49, 50) When accounting for a 7% loss to follow-up rate, 250 women per arm will yield N=232 evaluable subjects. With N=232 evaluable samples per arm, we achieve 80.7% power to detect a 4.3% absolute difference in our primary endpoint, which is the proportion of vertical transmission of CT/NG, between the two groups, using a one-sided Fisher's Exact test, at a 0.05 significance level.

Methods for minimizing bias

Enrollment statistics, including total number of women attending their first antenatal clinic visit, total enrolled, total ineligible, and total who declined to participate, will be recorded in a weekly tally sheet and presented at bimonthly study meetings. Participant characteristics, such as sociodemographic characteristics, gestational age, HIV infection status, syphilis test results, obstetric history (e.g. history of preterm birth), in the testing and standard-of-care clinics will be monitored and compared to assess balance. Attrition will also be monitored and attrition bias will be assessed on a monthly basis.

Data Management

Data will be collected and managed using REDCap electronic data capture tools hosted at the Botswana Harvard AIDS Institute Partnership (BHP). REDCap (Research Electronic Data Capture) is a secure, web-based software platform designed to support data capture for research studies, providing 1) an intuitive interface for validated data capture; 2) audit trails for tracking data manipulation and export procedures; 3) automated export procedures for seamless data downloads to common statistical packages; and 4) procedures for data integration and interoperability with external sources.

Data will be entered offline at study clinics into CRFs on the REDCap mobile application on study tablets. At the end of each working day, data will be checked for any errors, discrepancies and missing data

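### The 80.7% power treats 464 women as independent although care follows the clinic attended, and the clinic-level primary analysis names no test and no method for within-clinic correlation

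*SAP*

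**What the plan says.** Exposure is fixed by clinic. Under Specific Aim 1, Protocol Section 3 states "We will recruit 250 study participants from pregnant women presenting for antenatal care services at designated study" testing clinics. Under Specific Aim 2, a further 250 women at standard-of-care "clinics will be enrolled as a comparison group receiving the standard care with additional partner services". Protocol Section 7a confines all study recruitment to no more than eight clinics. It does not give the number per arm, and Aims 1 and 2 could use fewer than eight.

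The SAP's Sample size paragraph takes 250 women per arm, 7% loss and so 232 evaluable per arm, with 5% transmission under standard care and 0.7% with testing. It concludes "we achieve 80.7% power to detect a 4.3% absolute difference in our primary endpoint". The test assumed for that figure is Fisher's exact, one-sided at 0.05. The paragraph gives no ICC, design effect, clinic count or clinic size.

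The SAP's Statistical analysis section says the primary outcome "will be assessed using intention to treat analysis at the clinic level". Unadjusted and adjusted analyses are planned, the latter "including risk factors for maternal STI and neonatal infection that may be imbalanced between the testing and standard-of-care clinics". It adds: "Effect measures will be estimated with 95% confidence intervals". No test, model or effect measure is named for the primary outcome. Under Methods for minimizing bias, participant characteristics "in the testing and standard-of-care clinics will be monitored and compared to assess balance".

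**The concern.** When care is set by clinic, women in the same clinic may share local prevalence, partner networks and quality of care, so their outcomes need not be independent. A power calculation and a test that count 464 separate women then claim more information than the design may provide.

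The clinic-level wording can be read in two ways, and the plan is incomplete under both. It may mean that women are analysed according to their clinic's assignment. Fisher's test could then be the unadjusted comparison, but nothing allows for correlation. Or it may mean that clinics are the units, in which case a power figure for individual women belongs to a different test. Adjusting for imbalanced risk factors and monitoring balance deal with confounding; they supply neither a variance that reflects clinics nor the right degrees of freedom.

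At stake are the error rate and interval width for the primary endpoint, and the freedom to choose a method after the data are seen.

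**Working it through.** **Inputs from the documents.** n = 232 per arm (250 × 0.93 = 232.5), p_C = 0.05, p_T = 0.007, one-sided 0.05 (SAP, Sample size); at most eight clinics (Protocol 7a).

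**Assumptions.** The documents give no ICC and no split. I use ICC 0, 0.001, 0.005 and 0.01 with beta-binomial clinic counts, and 4, 3 or 2 equal clinics per arm (58, about 77, or 116 women each). Four per arm is the equal split of the maximum of eight.

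**1. The plan's figure.** One-sided normal approximation with continuity correction: power = Φ[(d − 1/n − 1.645·se0)/se1].
- d = 0.043; 1/n = 0.00431.
- se0 = √(2 × 0.0285 × 0.9715/232) = 0.01545.
- se1 = √((0.05 × 0.95 + 0.007 × 0.993)/232) = 0.01532.
- The argument is 0.867 and Φ = 80.69%, matching 80.7%.

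No clustering term is needed to reach it. Exact enumeration of the one-sided Fisher test gives 85.2%, so the printed figure is conservative for independent women.

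**2. Reading (a): women analysed with no clinic term.** Each arm's total is the exact convolution of its clinics' beta-binomial counts. Power is at 5% vs 0.7%; size and coverage are at 5% vs 5%. Coverage is for a Newcombe 95% interval for the risk difference (an assumption, since the SAP names no interval).

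| One-sided Fisher, ICC: | 0 | 0.001 | 0.005 | 0.01 |
|---|---|---|---|---|
| Power, 4 per arm | 85.2% | 84.6% | 82.5% | 80.5% |
| Power, 2 per arm | 85.2% | 84.0% | 80.5% | 77.5% |
| Size, 4 per arm | 3.3% | 3.7% | 5.2% | 7.0% |
| Size, 3 per arm | 3.3% | 3.8% | 5.8% | 8.2% |
| Size, 2 per arm | 3.3% | 4.0% | 7.0% | 10.3% |
| 95% CI coverage, 4 per arm | 95.2% | 94.6% | 92.0% | 88.7% |
| 95% CI coverage, 2 per arm | 95.2% | 93.9% | 88.7% | 82.6% |

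Size passes 5% above ICC 0.0046 (4 per arm), 0.0034 (3) or 0.0023 (2).

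**3. Reading (b): clinics as units.** One candidate is the pooled t-test on raw clinic proportions, t = (mean_C − mean_T)/[s·√(1/k_C + 1/k_T)] on k_C + k_T − 2 degrees of freedom, with k the number of clinics in each arm. Power from 200,000 simulations:

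| Equal split, ICC: | 0 | 0.001 | 0.005 | 0.01 |
|---|---|---|---|---|
| 4 per arm | 82% | 80% | 74% | 67% |
| 3 per arm | 76% | 74% | 65% | 57% |
| 2 per arm | 62% | 59% | 50% | 43% |

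With 2 per arm, about 4% of trials at ICC 0 have no between-clinic variance and are counted as significant; not counting them gives 58%. The size of this test stays at 4.8–5.0% (4 per arm) and 5.4–5.5% (2 per arm).

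The split matters as much as the ICC. With 3 control and 5 testing clinics, power is 88/87/81% at ICC 0/0.001/0.005; the reverse split gives about 67% at ICC 0. The choice of test matters too: an arcsine-transformed t-test with 3 per arm reaches about 80% at ICC 0.

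**4. Sparse events.** Expected events are 232 × 0.05 = 11.6 and 232 × 0.007 = 1.6. The chance of none in the testing arm is 0.993^232 = 20% at ICC 0, so some standard models could fail.

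**The case against.** The strongest reply is that clinic-level intention to treat most naturally means analysing women by their clinic's assignment. Fisher's test, the only one named for this endpoint, would then be the unadjusted analysis. Its power stays close to 80.7% across the assumed ICCs, and its own conservatism keeps the size below 5% at low ICC. That stands: on this reading the trouble is type I error and coverage at higher ICCs, not a power shortfall. It does not close the gap, because Fisher appears only in the sample-size paragraph and ignores clinic.

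The upper ICCs can also be called severe. The between-clinic CV is √[ICC(1 − p)/p], so ICC 0.01 means 44% at a 5% rate but 119% at 0.7%. This is a fair caution. Holding the CV at its 5%-rate value in both arms, however, moves t-test power with 4 per arm only from 67% to 69%.

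Finally, Protocol Section 21 schedules CT/NG enrolment for February 2021 to March 2022, and no added enrolment is proposed here, so a restated power changes little in the design. That is also fair; the analysis wording matters most.

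A reader might infer from the equal-split t-test table that the stated power is reached only with four clinics per arm and almost no correlation. The documents do not support this: they fix neither the test nor the split, and 3 control with 5 testing clinics gives more than 80.7% even at ICC 0.005.

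**Conclusion.** The omission is certain: care follows the clinic, the 80.7% has no clinic allowance, and the primary analysis names neither a test nor a method for within-clinic correlation. This should be fixed.

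The size of the consequence is conditional on an ICC, a test and a clinic split that the documents leave open. With no clinic term, the harm is negligible near ICC 0.001 (size 3.7% to 4.0%, coverage about 94% to 95%). It becomes real from roughly 0.0023 to 0.005 upward, depending on the number of clinics, and reaches a size of 7.0% to 10.3% at 0.01. With clinics as units, the stated power belongs to another test, and the true figure may lie above or below it.

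Two further inferences would go too far. The 80.7% is not an arithmetic error, since it understates exact one-sided Fisher power under independence. Nor do the documents show that the false-positive rate will exceed 5%, because no ICC is given.

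A secondary point: a conventional two-sided 95% interval corresponds to a two-sided 0.05 test, whereas the powered test is one-sided at 0.05. Exact two-sided Fisher power is 76.4%, so in about 8.7% of trials of independent women only the one-sided test would be significant.

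**What to change.** In the SAP's Statistical analysis section, say what clinic level means and name one primary analysis that accounts for clinic and copes with few clinics and sparse or zero events. Examples are a comparison of clinic-level proportions on clinic degrees of freedom, or an individual-level model clustered by clinic with a small-sample correction. State its sidedness and report an interval that matches its alpha.

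In the Sample size section, replace 80.7% with the power of that analysis, stating clinics per arm, women per clinic and a range of assumed ICCs that includes values near zero.

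The cost is a few sentences and a power recalculation, probably by simulation because events are sparse. The stated power may be lower and the intervals wider. No extra enrolment is proposed.
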